## **6.2.5 Baseline Characteristics**

Baseline characteristics include (1) demographics and other relevant baseline characteristics, (2) baseline disease characteristics (i.e., migraine history, cardiac and other risk factors, prior triptan response, and current triptan response), (3) medical history, and (4) prior non-study medications. Baseline characteristics are tabulated for each of the following analysis set sets:

- Safety analysis set
  - Baseline characteristics (1) through (4)
  - Demographics and other relevant baseline characteristics, and migraine history by subgroup level and overall by all subgroups of interest defined in Section 4.3
- Enrolled analysis set but not in the safety analysis set: Demographics and other relevant baseline characteristics, and migraine history
- Migraine analysis set: Demographics and other relevant baseline characteristics, and migraine history.

Baseline for a parameter (e.g., weight) is defined according to analysis set as follows:

- Enrolled analysis set but not in the LTT participated analysis set: Last non-missing value
- LTT participated analysis set but not in the safety analysis set: Last non-missing value on or before the IWRS baseline visit date

- Safety, migraine, and outcomes research analysis sets: Last non-missing value in the pre-treatment analysis period; see Sections 7.1 and 7.2).

“Last” is determined by the measurement date/time. Other criteria such as last entry date/time may be applied to break ties on the same measurement date, as available from CRF data. See Sections 6.4.2.3, 6.4.3.1, 6.4.4.1, and 6.5 for handling of ties on the same measurement date or time. Note that the baseline value of a parameter is independent of the baseline analysis visit defined in Table 3; the latter is used only in by-subject listings that display visit, and in COVID-19 analyses by analysis visit (see Sections 6.6.2 and 6.6.3).

By-subject listings are provided for the enrolled analysis set for the following: demographics; medical history; migraine history; cardiac and other risk factors for subjects with any risk factor present; prior triptan response; and current triptan response. Refer to the Zavegeptan Core SAP for additional details.

#### **6.2.5.1        *Demographics and Other Relevant Baseline Characteristics***

Refer to the Zavegeptan Core SAP for the table of demographics and other relevant baseline characteristics. Previous study participation (e.g., any study, BHV3500-201, BHV3500-301) is also displayed.

#### **6.2.5.2        *Baseline Disease Characteristics***

Refer to the Zavegeptan Core SAP for tables of migraine history, cardiac and other risk factors, prior triptan response, and current triptan response.

#### **6.2.5.3        *Medical History***

Medical history is tabulated by system organ class (SOC) and PT, and displayed in descending order of overall frequency within SOC and PT.

#### **6.2.5.4        *Prior Medications***

The following non-study medications are tabulated by therapeutic class and preferred name for the safety analysis set:

- Prior medications: all; migraine standard of care; prophylactic migraine
- Current medications: all; migraine standard of care; prophylactic migraine
- Pre-LTT medications: all; migraine standard of care; prophylactic migraine
- OP medications: all; migraine standard of care; prophylactic migraine.

Medications are displayed in descending order of overall frequency within therapeutic class and preferred name. See Section 6.2.6.3.

Refer to the Zavegeptan Core SAP for the definitions of prior and concurrent medications.

Pre-LTT medications are defined as those taken on or after informed consent and before LTT start, i.e., those meeting any of the following criteria:

- Informed consent date  $\leq$  imputed start date or imputed stop date  $\leq$  LTT start date – 1
- Informed consent date  $\leq$  imputed start date or imputed stop date, and LTT start date is missing
- Imputed start date  $\leq$  informed consent date  $<$  LTT start date – 1  $\leq$  imputed stop date
- Imputed start date  $\leq$  informed consent date  $\leq$  imputed stop date, and LTT start date is missing.

OP medications are defined as those taken during the OP, i.e., those with (1) OP start date  $\leq$  imputed start date or imputed stop date  $\leq$  OP end date, or (2) imputed start date  $\leq$  OP start date  $\leq$  OP end date  $\leq$  imputed stop date.

### **6.2.6      *Exposure***

Study drug is zavegepant 10 mg IN spray.

Subjects provide study drug taken status (yes, no), number of sprays administered, and nostril location of each spray (left, right) in the eDiary every day after they are determined to be eligible to take study drug. Sites may enter this information on the eDiary medication reconciliation form for missed doses. Days on which a subject took study drug are determined by records with non-missing study drug date/time (see Section 7.1). If there are no study drug data in the eDiary on a given day, then it is assumed that the subject did not take study drug that day.

Study drug accountability is provided by the site on the Drug Accountability CRF. There are 4 single-use devices in each kit. Sites provide the number of unused devices in each kit dispensed and returned.

#### **6.2.6.1      *Study Therapy***

A by-subject listing presents eDiary study drug exposure and study drug accountability for the full analysis set as follows:

- Study day and treatment day derived respectively from eDiary study drug dates and drug accountability kit dispensed dates
- eDiary: study drug date/time, source (evening report or medication reconciliation form), number of sprays administered, nostril location of each spray. Only eDiary records with non-missing study drug date/time and number of sprays  $> 0$  are displayed.
- Drug accountability: kit dispensed and kit returned status (yes, no), kit dispensed date, kit returned date, kit ID, all investigational product (IP) used status (yes, no), number of IP devices not used. Invalid kit IDs are identified.

The listing also displays COVID-19 visit impact code for visits impacted by COVID-19 (see Section 9.1.5.2).

Another by-subject listing presents eDiary study drug exposure (i.e., total number of sprays administered) by nostril location (left, right, total) by month during the LTT for the safety analysis set. This also displays cumulative zavegepant exposure from both sources (i.e., eDiary and drug accountability), and identifies subjects with  $\geq 10$  cumulative absolute spray difference between the 2 sources.

An administrative listing of IP batch numbers is provided for the safety analysis set. Refer to the Zavegepant Core SAP for listing contents.

### **eDiary Zavegepant and LTT Exposure**

eDiary zavegepant and LTT exposure is tabulated as continuous or categorical variables for the safety analysis set, and includes the following parameters:

- Time in the OP (weeks), derived as  $(OP\ end\ date - OP\ start\ date + 1)/7$
- Time from LTT start to last contact (weeks), derived as  $(last\ contact\ date - LTT\ start\ date + 1)/7$
- Time in the LTT period (weeks), derived as  $(LT\ end\ date - LT\ start\ date + 1)/7$
- Time in the LTT period (weeks) categories:  $\geq 11$ ,  $\geq 23$ ,  $\geq 51$ . These correspond to using a 1-week lower bound on 3, 6, and 12 months, respectively.
- Time on zavegepant (weeks), derived as  $(study\ drug\ end\ date - study\ drug\ start\ date + 1)/7$
- Time on zavegepant (weeks) categories:  $<12$ ,  $\geq 12$  to  $< 24$ ,  $\geq 24$  to  $< 36$ ,  $\geq 36$  to  $< 48$ ,  $\geq 48$ . These align with subgroups specified in Section 4.3.
- Cumulative zavegepant exposure (sprays), derived by summing number of sprays across records with complete study drug dates
- Cumulative zavegepant exposure (sprays) categories:  $< 20$ ,  $\geq 20$  to  $< 40$ ,  $\geq 40$  to  $< 60$ ,  $\geq 60$  to  $< 80$ ,  $\geq 80$ . These align with subgroups specified in Section 4.3.
- Average zavegepant exposure (sprays per month), derived as (1) cumulative zavegepant exposure (sprays) if time in the LTT period  $< 2$  weeks, or (2)  $4 \times$  cumulative zavegepant exposure/time in the LTT period if time in the LTT period  $\geq 2$  weeks.
- Average zavegepant exposure (sprays per month) categories:  $< 6$ ,  $\geq 6$ . These align with subgroups specified in Section 4.3.
- Number and percentage of subjects who administered  $> 1$  spray on any 1 day
- Number and percentage of subjects who administered  $> 8$  sprays per month in any month
- Exposure categories, defined as the number and percentage of subjects who administered
  - $\geq 1$  spray per month for 1, 2, 3, 4, 5,  $\geq 12$ ,  $\geq 6$ ,  $\geq 3$  and  $\geq 1$  months
  - $\geq 2$  sprays per month for 1, 2, 3, 4, 5,  $\geq 12$ ,  $\geq 6$ ,  $\geq 3$  and  $\geq 1$  months
  - $\geq 3$  sprays per month for 1, 2, 3, 4, 5,  $\geq 12$ ,  $\geq 6$ ,  $\geq 3$  and  $\geq 1$  months

- $\geq 4$  sprays per month for 1, 2, 3, 4, 5,  $\geq 12$ ,  $\geq 6$ ,  $\geq 3$  and  $\geq 1$  months
- $\geq 5$  sprays per month for 1, 2, 3, 4, 5,  $\geq 12$ ,  $\geq 6$ ,  $\geq 3$  and  $\geq 1$  months
- $\geq 6$  sprays per month for 1, 2, 3, 4, 5,  $\geq 12$ ,  $\geq 6$ ,  $\geq 3$  and  $\geq 1$  months
- $\geq 7$  sprays per month for 1, 2, 3, 4, 5,  $\geq 12$ ,  $\geq 6$ ,  $\geq 3$  and  $\geq 1$  months
- $\geq 8$  sprays per month for 1, 2, 3, 4, 5,  $\geq 12$ ,  $\geq 6$ ,  $\geq 3$  and  $\geq 1$  months.
- Total zavegepant exposure (sprays) summed across all subjects, derived by summing cumulative exposure across all subjects
- Total zavegepant exposure (patient-years), derived by summing (study drug end date – study drug start date + 1)/365.25 across all subjects.

See Section 7.1 for derived dates.

eDiary zavegepant and LTT exposure is also tabulated by subgroup level and overall for the safety analysis set for all subgroups of interest described in Section 4.3.

Months are 4-week (28-day) intervals in the LTT analysis period defined as follows:

- Month 1 ( $\leq 4$  weeks; study days 1 to 28)
- Month 2 ( $> 4$  to  $\leq 8$  weeks; study days 29 to 56)
- Month 3 ( $> 8$  to  $\leq 12$  weeks; study days 57 to 85)
- Month 4 ( $> 12$  to  $\leq 16$  weeks; study days 85 to 112)
- Month 5 ( $> 16$  to  $\leq 20$  weeks; study days 113 to 140)
- Month 6 ( $> 20$  to  $\leq 24$  weeks; study days 141 to 168)
- Month 7 ( $> 24$  to  $\leq 28$  weeks; study days 169 to 196)
- Month 8 ( $> 28$  to  $\leq 32$  weeks; study days 197 to 224)
- Month 9 ( $> 32$  to  $\leq 36$  weeks; study days 225 to 252)
- Month 10 ( $> 36$  to  $\leq 40$  weeks; study days 253 to 280)
- Month 11 ( $> 40$  to  $\leq 44$  weeks; study days 281 to 308)
- Month 12 ( $> 44$  to  $\leq 48$  weeks; study days 309 to 336)
- Month 13 ( $> 48$  to  $\leq 52$  weeks; study days 337 to 364)
- Month 14 ( $> 52$  to  $\leq 56$  weeks; study days 365 to 392).

See Section 7.3 for the definition of study days.

Exposure categories assess the number of months in which a subject exceeded select spray counts in the LTT analysis period (see Section 7.2), where the number of months are not necessarily consecutive. For example, suppose a subject administers 4 sprays in Month 1, 3 sprays in Month 2, 5 sprays in Month 3, 6 sprays in Month 4, and 0 sprays in Month 5. Thus, this

subject is considered to have administered  $\geq 2$  sprays per month for 4 months (i.e., Months 1 through 4),  $\geq 4$  sprays per month for 3 months (i.e., Months 1, 3 and 4), and  $\geq 6$  sprays per month for 1 month (i.e., Month 4).

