### **eDiary Zavegepant Sprays per Month Over Time**

eDiary zavegepant sprays per month over time are tabulated as a continuous variable at each month in the LTT analysis period for the safety analysis set. This analysis is based on absolute spray counts per month. Using the example above for exposure categories, the subject has 4, 3, 5, 6, and 0 sprays per month in Months 1 through 5, respectively, and 5 months in the LTT period as determined by calculating the ceiling([LTT end date – LTT start date + 1]/28).

This is also tabulated for the safety analysis set with  $\geq 51$  weeks in the LTT period.

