#### **6.4.6 Migraine Days per Month**

Subjects report migraine status (yes, no, unable to recall) and intensity (mild, moderate, severe, unable to recall) every day in the eDiary evening report. Sites may provide these data on the eDiary medication reconciliation form.

Migraine days per month are assessed as “migraine days per 4 weeks” to correspond with the 4-week visit schedule. Analyses are based on the OP and LTT analysis periods for the migraine analysis set, i.e., subjects in the safety analysis set with  $\geq 14$  days of data (not necessarily consecutive) in both the OP analysis period and  $\geq 1$  month (4-week interval) in the LTT analysis period.

- A day of data is defined as an eDiary record with complete date and {yes or no} response to having a migraine. If a subject has multiple responses or migraine severities on the same date, then the most severe migraine last sequenced is chosen. Only days of data are included in analyses.
- A migraine day is defined as a day of data with a “yes” response to having a migraine.
- A treated migraine day is defined as a migraine day on which zavegeptan is administered.
- Months are defined as 4-week (28-day) intervals in the LTT analysis period. See Section 6.2.6.1 for the definition of months.

Thus, the total numbers of days of data and migraine days are calculated for the OP analysis period and for each month in the LTT analysis period.

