#### 6.4.6.2 *Treated Migraine Days per Month*

The number of treated migraine days per month is derived as follows:

- Month during LTT:
  - If the total number of study days in the month < 14: total number of treated migraine days in the month (i.e., no proration)
  - If the total number of study days in the month  $\geq 14$ :  $28 \times (\text{total number of treated migraine days in the month}) / (\text{total number of study days in the month})$
- Overall LTT:
  - If the total number of study days in the LTT analysis period < 14: total number of treated migraine days in the LTT analysis period (i.e., no proration)
  - If the total number of study days in the LTT analysis period  $\geq 14$ :  $28 \times (\text{total number of treated migraine days in the LTT analysis period}) / (\text{total number of study days in the LTT analysis period})$ .

All study days from LTT start to LTT end are included in analyses, not only days of data.

The following tables are produced for the safety analysis set:

- Number and percentage of subjects in the following categories based on the number of treated migraine days per month in the overall LTT by migraine intensity (total; moderate or severe): 0,  $> 0$  to  $< 1$ ,  $\geq 1$  to  $< 2$ ,  $\geq 2$  to  $< 3$ ,  $\geq 3$  to  $< 4$ ,  $\geq 4$  to  $< 5$ ,  $\geq 5$  to  $< 6$ ,  $\geq 6$  to  $< 7$ ,  $\geq 7$  to  $< 8$ ,  $\geq 8$ ,  $< 2$ ,  $\geq 2$ . The last 2 categories for total migraine intensity align with subgroups specified in Section 4.3.
- Number and percentage of subjects in the above categories based on the maximum number of treated migraine days per month in any 1 month during LTT by migraine intensity.

These tables are also produced for the safety analysis set with  $\geq 51$  weeks in the LTT analysis period (see Section 6.2.6.1).

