  - Estimated glomerular filtration rate (eGFR) according to the re-expressed abbreviated (4-variable) Modification of Diet in Renal Disease (MDRD) Study equation  $\leq 40$  mL/min/1.73m^2 during pre-LTT \*
  - BMI  $\geq 33$  kg/m^2 during pre-LTT \*
  - S-STS total score  $> 0$  during pre-LTT.

For the subcategories marked with “\*”, all non-missing values during the pre-LTT analysis period must meet the deviation criteria in order to be considered a deviation.

Relevant subject management protocol deviations include the following categories:

- Study drug dosing error, defined as any of the following subcategories:
  - Study drug taken but not participated in the LTT phase
  - Administered  $> 1$  spray on any 1 day (see Section 6.2.6.1)
  - Administered  $> 8$  sprays per month in any 1 month (see Section 6.2.6.1).
- eDiary site or subject usage compliance  $< 80\%$  from LTT start to end (see Section 6.2.6.2)
- Prohibited non-study medications, defined as any of the following subcategories:
  - Atypical antipsychotics, divalproex, valproic acid, or valproate taken on or after informed consent #
  - Barbiturate taken up to 14 days before LTT start or afterward #
  - Butterbur root or extract taken up to 14 days before LTT start or afterward
  - Ergotamine, lasmitidan, or triptan taken up to 2 days before LTT start or afterward #
  - Gepant taken on or after informed consent #
  - Lamotrigine taken on or after informed consent
  - Medication administered nasally (1) anytime during pre-LTT, or (2) for  $\geq 10$  days (not necessarily consecutive) per month on or after LTT start #. Route must be nasal. For criterion (2), the following applies:

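### SAP 6.2.6.1 prints Month 3 one day too long (Days 57 to 85), so Day 85 is also in Month 4; if coded as printed, a few Month 3 outputs would be slightly wrong

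*SAP*

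**What the plan says.** The months are defined in SAP Section 6.2.6.1, under the subheading on eDiary zavegepant and LTT exposure. A month is 4 weeks, or 28 days, and 14 months are listed, each with limits in weeks and in study days. Month 3 covers the time above 8 and up to 12 weeks and is printed as "study days 57 to 85". Month 4 covers the time above 12 and up to 16 weeks and is printed as "study days 85 to 112". Section 7.3 makes the LTT start date Study Day 1.

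The following subsection, on sprays per month over time, gives a worked example with "5 months in the LTT period as determined by calculating the ceiling" of the LTT days divided by 28.

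Several outputs use these months:

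- **Section 6.2.6.1:** a listing of sprays "by nostril location (left, right, total) by month during the LTT for the safety analysis set", which also shows cumulative exposure; the row for subjects with more than 8 "sprays per month in any month"; the exposure categories; and sprays by month over time.
- **Section 6.4.6:** "Months are defined as 4-week (28-day) intervals in the LTT analysis period", with a pointer back to 6.2.6.1. This feeds migraine days by month (6.4.6.1) and the table of the "maximum number of treated migraine days per month in any 1 month during LTT by migraine intensity" (6.4.6.2).
- **Section 9.2:** the dosing-error deviation for more than 8 "sprays per month in any 1 month (see Section 6.2.6.1"), and the deviation for nasal medication on 10 or more days in a 4-week month, which also cites 6.2.6.1.

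**The concern.** A list of 28-day intervals should assign each study day to exactly one month. Here one interval has 29 days and Day 85 has two homes. The list is the SAP's only day-by-day definition of a month, other sections refer back to it, and explicit day ranges are easily copied into a program.

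At stake is the accuracy of several Month 3 results, and possibly Month 4 results. Spray counts are compared with a threshold of 8 and nasal-medication days with a threshold of 10, both without proration, so one extra day can carry a subject over a limit. Treated migraine days are prorated by the study days in the month, so an extra day can pull a value below a category boundary. A wrong value of this kind would look plausible in a table and would not be noticed.

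**Working it through.** **1. The printed grid.** Under the 28-day rule, Month k covers Days 28(k − 1) + 1 to 28k. Thirteen of the 14 printed rows match. Only Month 3 does not.

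| | Printed | Length | 28-day rule |
|---|---|---|---|
| Month 2 | 29 to 56 | 28 | 29 to 56 |
| Month 3 | 57 to 85 | 85 − 57 + 1 = 29 | 57 to 84 |
| Month 4 | 85 to 112 | 28 | 85 to 112 |

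The printed lengths add up to 13 × 28 + 29 = 393 for a grid of 14 × 28 = 392 days. Day 85 is the only day in two months, and no day is left out.

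**2. Which bound is meant.** Twelve weeks is 12 × 7 = 84 days. By the month-count rule, ceiling(84/28) = 3 and ceiling(85/28) = 4. Both put Day 85 in Month 4 only. With Month 3 ending on Day 84, the grid covers Days 1 to 392 once each.

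**3. What literal coding could do.** The printed ranges can be programmed in three ways:

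- (a) Day 85 counts in both months.
- (b) Each day goes to the first matching month. Month 3 then has 29 days and Month 4 has 112 − 86 + 1 = 27.
- (c) Each day goes to the last matching month. Month 3 then ends on Day 84 and nothing is wrong.

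**4. Examples under (a) or (b).**

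- *More than 8 sprays.* Take 8 sprays on Days 57 to 84, one on Day 85, and no 28-day SAP month above 8. Printed Month 3 holds 8 + 1 = 9, so the subject enters the more-than-8 row and the dosing-error deviation.
- *The reverse, under (b) only.* Take 9 sprays on Days 85 to 112, one of them on Day 85, and no other month above 8 under the printed grid. Month 4 falls to 8 and a correct flag is lost.
- *Nasal medication.* Daily use on Days 76 to 85 gives 84 − 76 + 1 = 9 days in the 28-day Month 3 and 1 day in Month 4. Printed Month 3 holds 10, which meets the deviation criterion.
- *Treated migraine days.* Eight treated days in Month 3, none on Day 85, should give 28 × 8/28 = 8. With 29 study days the value is 28 × 8/29 = 7.72, which is in the category from 7 to below 8. In the maximum-month table this changes the subject's category only if no other month reaches 8.
- *Monthly spray counts.* At a constant daily rate, mean Month 3 sprays would be 29/28 of the correct value, or 1/28 = 3.6% too high. Under (a), the monthly totals in the listing would also exceed the cumulative count beside them by the sprays taken on Day 85.

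**5. What does not use the grid.** Cumulative sprays are summed over all records. Average sprays divide that sum by time in the LTT period. Patient-years come from study drug dates. The Section 4.3 subgroups use these quantities, time on drug, overall-LTT treated migraine days, or baseline and medication characteristics. The primary endpoints use the on-treatment safety period.

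**The case against.** The strongest reply is that this is a typographical slip that the SAP already resolves. The 28-day rule, the 12-week limit on the same line, the start of Month 4 and the division by 28 all agree on Day 84, and nothing in the documents shows that any program follows the misprint. This stands. It makes every consequence conditional, but it does not make the printed line correct, and other sections cite that line as the definition.

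A second reply is that the flagged behaviour may be real. If none of the 8 sprays on Days 57 to 84 fell on Day 57, then Days 58 to 85 hold 9 sprays in 28 consecutive days. The nasal example is likewise a genuine 10-day course. This is also fair. The results are wrong only against the SAP's fixed months, but those are the months on which the SAP says it reports.

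A reader might go further and infer that a sizeable, calculable number of subjects would be misclassified. The documents do not support that:

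- **Coding.** Under (a), Month 3 flags are added and Month 4 is untouched. Under (b), gains in Month 3 are partly offset by losses in Month 4. Under (c), there is no effect.
- **Usage.** Protocol Section 7.2.2 caps use at 8 per 28 days, and Section 6.6 discontinues subjects who average fewer than 2 doses per month over 3 consecutive months. Neither document gives an expected rate.
- **Retention.** Dropout before Day 85 removes affected subjects. Dropout afterwards leaves fewer months to compete with Month 3 for the maximum, which works the other way in that table.

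**Conclusion.** The printed Month 3 range is wrong: it has 29 days and shares Day 85 with Month 4. The intended end is Day 84. Results would be affected only if the printed range is coded and Day 85 is placed in Month 3, either as well as or instead of Month 4. The outputs exposed are then the more-than-8-sprays flag and deviation, the monthly spray counts and exposure categories, the nasal-medication deviation, and the by-month migraine-day and treated-migraine-day results.

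The effect is small. No subject count should be attached to it, because it depends on the coding choice and on usage and retention that the documents do not give. It would also be wrong to infer that the study's safety conclusions or overall exposure are in doubt, since the primary endpoints, cumulative, average and patient-year exposure, and Section 4.3 subgroup membership do not depend on these months. Severity is minor. Confidence in the arithmetic is high.

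**What to change.** In SAP Section 6.2.6.1, change the Month 3 range to study days 57 to 84. Then confirm, and document, that the programs for exposure, for the spray and nasal-medication deviations, and for migraine days use that bound and assign Day 85 to Month 4 only.

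The cost is one digit in the SAP and a program check. No data collection, threshold, category label or clinical rule changes.
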